1 INTRODUCTION

Contact lens (CL) discomfort affects up to 50% of contact lens wearers.¹ Dry eye, in particular changes in meibomian gland (MG) structure and function, significantly increases the odds of CL drop out.² Studies have shown that managing meibomian gland dysfunction (MGD) results in positive outcomes for symptomatic contact lens wearers, including increased comfortable CL wear time.³

Launched in May 2018, the iLux® Device is a medical device approved in Canada for use by eye care professionals to provide in-office treatment for the management of MGD and evaporative dry eye disease (DED). The handheld device delivers localized heat (38-44°C) to the eyelids to melt meibum and the operator applies pressure to the treatment zone to express melted meibum through the gland orifices. The treatment can be applied to the upper and lower eyelids (sequentially) and takes 8-12 minutes to complete. Patient safety is maintained with the use of iLux® Smart Tips, which are sterile, single-use attachments to the handheld device which make contact with the eyelids during treatment.

The iLux® Device is considered comparable to another commercially available eyelid thermal pulsation system, the LipiFlow® System (Johnson & Johnson Vision). Previous studies have shown that treating MGD with a single LipiFlow® treatment increased mean comfortable CL wear time by 4 hours per day, which was sustained for up to 3 months.³

The purpose of this clinical trial is to investigate the efficacy of a single iLux® treatment in symptomatic CL wearers who have DED (according to the TFOS DEWS II diagnostic criteria),⁴ of the evaporative dry eye disease subtype (EDE).

2 OBJECTIVES

The objectives of this clinical trial are:

- To assess eye dryness symptoms (using the SPEED questionnaire) at 1- and 3-months post iLux® treatment;
- To assess Meibomian gland secretions (by expression using the Meibomian Gland Evaluator) at 1- and 3-months post iLux® treatment.

Primary endpoint:

- Changes in SPEED questionnaire score at 1 month.

Secondary endpoints:

- Meibomian gland secretion (assessments will be reported as meibomian gland scores (MGS));
- Pre-lens tear break-up time;
- Reported average wear time and comfortable wear time.

Exploratory endpoint:

- Changes in symptoms, determined using CLDEQ-8 and OSDI questionnaires, at 1- and 3-months, and SPEED at 3 months post iLux® treatment.

3 NULL HYPOTHESES

- There will be no difference between treatment and control groups for mean comfortable CL wear time.
- There will be no difference between treatment and control groups for symptoms, determined using SPEED questionnaire, at 1-month.
- There will be no difference between treatment and control groups for Meibomian gland score (MGS) at 1-month.

4 MATERIALS AND METHODS

4.1 STUDY DESIGN

4.1.1 OVERALL DESIGN

This is a prospective, single-site, parallel-group study involving 52 existing CL wearers who have confirmed EDE (according to the TFOS DEWS II diagnostic criteria). This study will involve three visits (Figure 1). Participants will attend CORE for a total of 3.5 hours.

Eligible participants will be randomized in a 1:1 ratio to receive a single, bilateral iLux® treatment at Visit 1 (treatment group), or delayed iLux® treatment provided at Visit 2 (control-treatment group i.e. 1-month no treatment, administer treatment at Visit 2). The treatment group will be reviewed 1- and 3-months after treatment. The control-treatment group will be reviewed at 1-month, at which point they will receive a single, bilateral iLux® treatment. The control-treatment group will be reviewed 1 month (full clinical assessment, including symptom assessment) and 3 months (symptom assessment only) after iLux® treatment. Participants randomized to the treatment group will be involved in the study for 3 months. Participants randomized to the control-treatment group will be involved in the study for 4 months.

Participants will wear their habitual CLs during the study. To ensure compliance, they will be supplied their habitual CLs and, if applicable, their habitual lens care products, for use during their involvement in the study.

[figure not shown]

Figure 1: Study flow chart

4.1.2 RANDOMIZATION

A randomization schedule will be generated using a web-based program: (www.randomization.com). The final study randomization schedule will be generated by CORE's Data Team Leader and provided to the research assistants for the study. Study investigators will remain masked to the randomization schedule until the study is completed and the database is locked.

4.1.3 MASKING

There will be no masking in this study.

4.2 STUDY POPULATION

4.2.1 SAMPLE SIZE CALCULATION

There are no current data available regarding the minimally clinically important differences for MGS nor SPEED scores to inform an effect size. Data from Blackie et al³ show a 12-point improvement in MGS score and 8-point improvement in SPEED scores with small standard deviations, corresponding to very large effect sizes of 1.7 and 1.8, respectively. This data supports a minimum sample of 9 in each group would be required to detect an 8-point mean difference in

SPEED scores at 90% power (alpha=0.05, power analysis = a priori, two-tailed, difference between two independent means).

However, an effect size of 1.7 and 1.8 are ambitious targets in this field. Applying targets of a more realistic effect size of 1.0 and a power of 90%, a minimum sample size of 23 in each group is recommended (alpha=0.05, power analysis = a priori, two-tailed, difference between two independent means). Factoring a 10% dropout, the total suggested sample size is 52 participants.

4.2.2 NUMBER OF PARTICIPANTS

Participants will be recruited using CORE records and advertising approved by the University of Waterloo Office of Research Ethics. Participants expressing an interest in the study will be pre-screened using the CLDEQ-8 questionnaire to assess whether they meet the symptomatic contact lens wear criteria. However, eligibility for the study can only be determined at the screening visit using the inclusion and exclusion criteria. Data from the pre-screening questionnaire will not be considered as study data and will be confidentially disposed of. This questionnaire will be repeated at the screening visit and stored as study data.

Up to 52 eligible participants will be randomized with a target of 46 participants completing the study. Informed consent will be obtained for all participants prior to their enrolment in the study.

4.2.3 INCLUSION AND EXCLUSION CRITERIA

A person is eligible for inclusion in the study if he/she:

1. Is at least 18 years of age and has full legal capacity to volunteer;
2. Has read and signed an information consent letter;
3. Is willing and able to follow instructions and maintain the appointment schedule;
4. Has been using the same CL type (brand, material and dimensions) for > 3 months;
5. Wears commercially available soft CLs on average >2 hours per day, 4-7 days per week;
6. Is willing to try to wear their habitual CLs on average \geq 6 hours per day, 4-7 days per week and maintain this for the duration of their involvement in the study;
7. Demonstrates an acceptable lens fit of their habitual contact lenses;
8. Does not have contact lens discomfort due to contact lens fit, lens material or known solution compatibility issues, in the opinion of the investigator;
9. Has at least one month supply of their habitual contact lens products at the time of the screening visit;
10. Has a CLDEQ-8 score \geq 12;

11. Has dry eye symptoms without CL wear (OSDI \geq 13) and has at least one of the two following signs:
 - a. Non-invasive tear break-up time (NITBUT) of < 10 seconds in at least one eye;
 - b. Fluorescein staining: > 5 spots of corneal staining OR > 9 conjunctival spots OR lid wiper staining (\geq 2mm length, \geq 25% width) in at least one eye;
12. Has a lipid layer thickness of \leq 100 nm in both eyes;
13. A meibomian gland secretion score (MGS) of \leq 15 for 15 glands of the lower lid in both eyes.

A person will be excluded from the study if he/she:

1. Is participating in any concurrent clinical or research study;
2. Has used any prescription systemic medications or topical treatments for MGD or dry eye for the past 30 days prior to the screening visit and not willing to stop using these for the study duration (excluding over-the-counter artificial tears, dietary supplements and ocular lubricants but includes warm compresses, eyelid massage, eyelid hygiene, manual meibomian gland expression, punctal plug insertion or punctal occlusion, intense pulsed light treatment of the face or eyelids);
3. Has previously received treatment with an eyelid thermal pulsation device;
4. Has a history of any of the following ocular (eye or eyelid) conditions or procedures in either eye within the past 90 days prior to the screening visit:
 - a. Ocular trauma
 - b. Chemical burns
 - c. Ocular *Herpes simplex* or *Herpes zoster* infection
 - d. Limbal stem cell deficiency
 - e. Recurrent ocular inflammation (e.g. uveitits, iritis, scleritis, episcleritis, keratitis)
5. Has undergone ocular surgery (e.g. intraocular, oculoplastic, corneal or refractive surgery procedure) within the past 12 months prior to the screening visit;
6. Has permanent make-up or tattoos on their eyelids;
7. Has any other known active* ocular disease and/or infection in either eye including: cicatricial lid margin disease or severe (\geq grade 3) blepharitis; moderate to severe (grade 2-4) allergic, vernal or giant papillary conjunctivitis; a hordeolum or styne; ocular surface abnormality that may compromise corneal integrity (e.g. Grade 3 corneal fluorescein staining, recurrent corneal erosion, corneal epithelial defect, map dot fingerprint dystrophy, previously treated chemical burn);

8. Has an eyelid abnormality that affects normal lid function (e.g. entropion, ectropion, oedema, blepharospasm, lagophthalmos, severe trichiasis, severe ptosis);
9. Has a systemic condition that in the opinion of the investigator may affect a study outcome variable;
10. Has any other condition that could compromise treatment or increase the risk of a procedure-related injury;
11. Is using any systemic or topical medications that in the opinion of the investigator may affect a study outcome variable;
12. Has known sensitivity to the diagnostic pharmaceuticals to be used in the study;
13. Has a history of sensitivity to rapidly blinking lights or photosensitive epilepsy;
14. Is pregnant, lactating or planning a pregnancy (by verbal communication) at the time of enrolment;
15. Is aphakic;
16. Is a member of CORE directly involved in the study;
17. Has taken part in a clinical research study within the last 30 days.

* For the purposes of this study, active ocular disease is defined as infection or inflammation which requires therapeutic treatment. Mild (i.e. not considered clinically relevant) lid abnormalities (blepharitis, meibomian gland dysfunction, papillae), corneal and conjunctival staining and dry eye are not considered active ocular disease. Neovascularization and corneal scars are the result of previous hypoxia, infection or inflammation and are therefore not active.

4.2.4 REPEATED SCREENINGS

In some circumstances, a repeated screening may need to be scheduled. Examples include, but are not limited to:

1. The participant attends having used any ocular lubricants (including artificial tears, emollients or liposomal sprays), used eye make-up or facial cosmetics around their eyes, rubbed their eyes and has been swimming in a chlorinated pool less than 12 hours prior to attending the screening visit;
2. Incomplete information available at time of screening to determine eligibility (e.g. current lens brands worn, history from current eye care practitioner etc.)
3. Study procedures unable to be completed in time scheduled for visit;
4. Study products not available at the time of the screening visit;

5. A transient health condition which may affect the eye(s) (e.g. a common cold, active allergies, fatigue etc.)
6. The short term use of medications (e.g. antibiotics, antihistamines etc.)
7. Reassessment of baseline ocular conditions (e.g. corneal and/or conjunctival staining, scars etc.)

The maximum total number of screenings permitted per participant will be 3.

4.3 STUDY MATERIALS

4.3.1 ILUX® DEVICE

One iLux® Device will be supplied by the study sponsor for use in this study (Figure 2). This device has been approved by Health Canada as a Class 3 medical device. Details of this device can be found in Table 1. iLux® treatment will be administered to eligible participants at either Visit 1 or Visit 2 (according to the randomization scheme).

Table 1: iLux® device details

iLux® Device	
Manufacturer	TEAR FILM INNOVATION, INC. [name]
Health Canada MDAL License #	101082
Device identifier	2020
Device class	Class 3

Figure 2: iLux® device with Smart Tip

4.3.2 ILUX® SMART TIPS

Single-patient-use, disposable iLux® Smart Tips will be used with the iLux® device (Table 2). These Smart Tips will be supplied by the sponsor for use in this study.

Table 2: iLux® Smart Tips details

iLux® Smart Tips	
Manufacturer	TEAR FILM INNOVATION, INC. [name]
Health Canada MDAL License #	101082
Device identifier	2020-D
Device class	Class 3

4.3.3 TOPICAL ANAESTHETIC

Prior to the iLux treatment, a topical anaesthetic eye drop, Alcaine, will be instilled into each eye (Table 3).

Table 3: Topical anaesthetic

Alcaine	
Manufacturer	Alcon Canada Inc., [name]
Health Canada, DIN	00035076
Active ingredient	Proparacaine hydrochloride (0.5%)
Non-medicinal ingredients	Glycerin, hydrochloric acid and/or sodium hydroxide (to adjust pH), purified water
Preservative	Benzalkonium chloride (0.01%)
Dosage	Instill one to two drops to the eye prior to iLux procedure.

4.3.4 CONTACT LENSES AND SOLUTIONS

Participants will wear their habitual contact lens type/ brand throughout the study and will continue to use their habitual lens care, if required. Participants will be instructed to wear their contact lenses for a minimum of 4 days per week, 6 hours per day throughout the study.

Participants will be instructed to bring their lens care system (if applicable) and an unopened package of their current contact lenses to the screening visit. The specifications of the contact lenses and care system will be noted.

Participants will be supplied with contact lenses and lens care solutions (as applicable) at the next scheduled visit after the screening visit.

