4.4.2 SCREENING (VISIT 1)

All participants who sign the informed consent letter will be assigned a study ID number. The investigator will determine participant eligibility using the inclusion and exclusion criteria. Ineligible participants will be discontinued from the study.

Participants will be instructed to refrain from the following for at least 12 hours before the screening visit:

- Used any ocular lubricants, artificial tears, emollients or liposomal sprays
- Using any eye make-up or facial cosmetics around their eyes
- Rubbing their eyes
- Swimming in a chlorinated pool

If participants attend the screening visit having used any of the products or performed any of the tasks listed above, they will be advised to reschedule their screening visit.

The following procedures will be conducted:

1. The participant is expected to attend the screening / baseline visit having refrained from CL wear for at least 12 hours. Participants are expected to bring a new pair of their habitual contact lenses and habitual solutions (if applicable)

2. The participant will be required to read and sign an Informed Consent Letter prior to enrollment. When the participant has signed the consent form, the participant will be considered enrolled in the study.
3. Participant demographics and medical history (age, sex, medical conditions, medications, allergies, management of dry eye symptoms).
4. Contact lens history: collect information regarding the participant's habitual CLs and lens care systems (if applicable). Also collect information on the participant's CL wear habits:
 - a. Average total wear time (number of days per week, number of hours per day)
 - b. Average comfortable wear time (number of hours per day).
5. The participant will complete the CLDEQ-8 questionnaire, SPEED questionnaire and OSDI questionnaire.
6. Monocular & binocular distance logMAR visual acuity (high contrast, high illumination) with habitual spectacles.
7. Non-invasive tear break-up time.
8. Lipid layer assessment (LipiView II)
9. Meibomian gland secretion assessment using the Meibomian Gland Evaluator.
10. Meibomian gland imaging of the upper and lower eyelids to determine meibomian gland drop out;
11. Ocular health assessment, including ocular surface staining.
12. Rinse eyes with saline to flush out any residual stain prior to lens insertion.
13. The participant inserts a new pair of their habitual contact lenses.
14. Contact lens fit assessment:

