 - a. Monocular & binocular distance logMAR visual acuity (high contrast, high illumination)
 - b. Lens wettability
 - c. Lens deposition
 - d. Centration
 - e. Movement
 - f. Tightness (push-up test)
 - g. Overall fit
15. After the lenses have been on eye for 10 minutes, pre-lens tear breakup time will be assessed.
16. The investigator will confirm that the participant meets the eligibility specifications set out in the inclusion criteria and exclusion criteria and is eligible to continue in the study.

17. If the participant meets all the inclusion criteria and none of the exclusion criteria, the participant will be randomized.
18. If the participant is randomized to the control-treatment group, the participant is advised to continue wearing their contact lenses on average ≥ 6 hours per day, 4-7 days per week until their next scheduled visit and to refrain from using any new OTC products or medications to manage their dryness and/or contact lens discomfort symptoms.
19. If the participant is randomized to the treatment group, the participant will immediately proceed to Visit 2.

The remaining visits outlined are separated according to treatment group assignment.

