6 POTENTIAL RISKS AND BENEFITS TO HUMAN PARTICIPANTS

This is a minimal risk study because of the use of marketed device and standard optometric assessments.

Contact lenses in this study will be worn on a daily wear basis, for at least 5 days per week and at least 6 hours per day. Adverse events and/ or complications in daily wear of soft contact lenses can occur (e.g. inflammation and infection). When contact lenses are worn on a daily wear basis, there is a small risk of an adverse event compared to not wearing contact lenses. When contact lenses are worn on an extended wear basis, there is a significantly increased risk of an adverse reaction compared with wearing contact lenses on a daily wear basis. As participants will be

wearing their habitual contact lens type in this study, there is no increased risk from wearing the lenses in this study. Due to the daily wear nature of the study, this study considered a non-significant risk study based on United States Food and Drug administration (FDA) and International Standards Organization (ISO) guidelines.

This study will provide participants with one treatment with the iLux® device. A safety study has found that iLux® treatment does not cause excessive heating of the cornea, outer eyelid or surrounding surface. It is possible that participants may experience: eyelid/eye pain requiring discontinuation of the treatment procedure, eyelid irritation or inflammation, temporary reddening of the skin, ocular surface irritation or inflammation (e.g., corneal abrasion, conjunctive oedema or conjunctival hyperemia), and ocular symptoms (e.g., burning, stinging, tearing, itching, discharge, redness, foreign body sensation, visual disturbance, sensitivity to light).

Additionally, it is possible that participants may experience temporary discomfort associated with the other study procedures including: burning and stinging, blurred vision, sandiness or grittiness, light sensitivity, dryness, itching, crusty eyes and foreign body sensation. The use of topical numbing (anaesthetic) eye drops may also cause stinging, burning or an allergic reaction. A dye (fluorescein) normally used for eye exams is being used in this study. Although rare, it is possible that participants may have any allergic reaction to the dye. This could cause discomfort to their eye.

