10 STATISTICAL ANALYSIS AND DATA MANAGEMENT

10.1 STATISTICAL ANALYSIS

All data will be analyzed by CORE at the University of Waterloo. Descriptive statistics will be provided on information regarding baseline variables (e.g. age, sex). The appropriate tests will be selected based on tests of normality; non-parametric tests will be used for data not showing a normal distribution. Analysis of variables will be conducted separately on each eye, and data will not be pooled. For assessments conducted for each eye separately, the right eye will be used for analysis if there is no difference between eyes.

The following planned comparisons of the key endpoints (SPEED scores, MGS, pre-lens tear break-up time, reported average wear time and comfortable wear time) will be made:

- Within group comparisons:
 - Baseline vs. 1 month [2-sided paired t-test or Wilcoxon signed rank test]
 - For treatment group only: Baseline vs. 1 month vs. 3 month [Repeated measures ANOVA or Friedman test]
 - Baseline vs. 1 month pooled data (i.e. treatment group and control-treatment group after 1 month treatment) [2-sided paired t-test or Wilcoxon signed rank test]
- Between group comparisons:
 - 1 month post-treatment vs. 1 month control (i.e. no treatment) [2-sided independent t-test or Mann-Whitney U test]

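### Baseline-to-follow-up tests of average lens wear time can pick up the 6-hour wear instruction as if it were an iLux effect

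*Combined protocol and SAP*

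**What the plan says.** **Entry.** Inclusion criterion 5 in section 4.2.3 reads: "Wears commercially available soft CLs on average >2 hours per day, 4-7 days per week". Criterion 6 asks separately for a person who "Is willing to try to wear their habitual CLs on average" at least 6 hours per day and will keep this up.

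**Instruction.** Section 4.3.4 applies to everyone: "Participants will be instructed to wear their contact lenses for a minimum of 4 days per week, 6 hours per day throughout the study". Step 18 of the screening visit (section 4.4.2) repeats it for one arm only. If allocated to the control-treatment group, "the participant is advised to continue wearing their contact lenses on average ≥ 6 hours per day, 4-7 days per week".

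**Baseline.** Step 4 of the same visit records lens-wear habits, including "Average total wear time (number of days per week, number of hours per day", and comfortable hours per day. The schedule has no run-in on the instruction before this.

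**Endpoint and tests.** Section 2 lists as secondary: "Reported average wear time and comfortable wear time". Section 10.1 counts both among the key endpoints and plans three comparisons with baseline: within group ("Baseline vs. 1 month [2-sided paired t-test or Wilcoxon signed rank test"), the treatment group across baseline, 1 and 3 months, and pooled data from both groups 1 month after treatment. It also plans a randomized comparison at 1 month, treated against not yet treated.

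**Wear days.** Section 6 describes wear "for at least 5 days per week and at least 6 hours per day", whereas section 4.3.4 gives 4 days.

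**The concern.** The baseline value describes what people did before the study, and every later value describes what they did under an instruction with a minimum. Criterion 6 matters mainly for people who do not yet wear lenses 6 hours a day, so the protocol allows for enrolling some of them. For those who comply, average wear time rises on entering the study, treated or not.

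A paired test cannot separate that rise from a treatment effect. The 3-month and pooled tests have no untreated comparator. Longer wear is a benefit readers will look for, so a significant increase from baseline could easily be reported as efficacy.

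**Working it through.** **The plan's own figure.** The documents give no figure for wear time; the only calculation is the sample size in section 4.2.1. A two-sample t-test with effect size 1.0, two-sided alpha 0.05 and power 0.90 needs 22.02 per group, rounded up to 23 (power 91.2%). With 10% dropout, 46 / 0.9 = 51.1, rounded up to 52. Both figures reproduce and neither is affected by this point. They supply the sample sizes used below: 23 completers per group, 46 pooled.

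**Inputs.** From the documents: entry above 2 h/day, instructed minimum 6 h/day. Assumed, because the documents do not give them: the share f entering below 6 h, their mean wear b, the SD s of individual change, and compliance.

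**One person.** The largest rise the rules allow is just under 6 − 2 = 4 h/day of total wear. A person already at 6 h or more need not change.

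**Group mean, no treatment effect, full compliance.**

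Rise = f × (6 − b)

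SD of change = √[s² + f(1 − f)(6 − b)²]

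For f = 25%, b = 4 h, s = 1 h: rise = 0.25 × 2 = 0.5 h/day; SD = √(1 + 0.1875 × 4) = 1.32 h. With b = 5 h the rise is 0.25 h/day, and with b = 3 h it is 0.75 h/day. If only half comply, each rise is halved.

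Chance that a two-sided paired t-test is significant although the treatment does nothing (b = 4 h):

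| Share below 6 h | Mean rise, h/day | s = 1 h: n = 23 / n = 46 | s = 2 h: n = 23 / n = 46 |
|---|---|---|---|
| 0% | 0 | 5% / 5% | 5% / 5% |
| 10% | 0.2 | 12% / 21% | 7% / 10% |
| 25% | 0.5 | 41% / 71% | 18% / 33% |
| 50% | 1.0 | 90% / 99.7% | 54% / 84% |

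**Simulation.** This used 8,000 runs, baseline wear from a normal distribution truncated to 2–16 h, SD of change 1 h, and compliers who start below 6 h raised to at least 6 h. With baseline SD 2 h and full compliance, the paired test is significant at n = 23 / n = 46 in 99% / 100% of runs for a baseline mean of 5 h, 79% / 98% for 6 h, 12% / 21% for 8 h, and about 5% for 10 h. With 50% compliance the 6 h case falls to 30% / 56%.

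**Pooled test.** The n = 46 figures take Visit 1 as baseline for everyone. Section 10.1 does not say whether the control-treatment group's baseline is Visit 1 or Visit 2B. At Visit 2B that group has already been under the instruction for about a month. If Visit 2B is used, and compliance does not change afterwards, the 0.5 h rise becomes (23 × 0.5 + 23 × 0) / 46 = 0.25 h/day.

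**Randomized 1-month test.** Both arms carry the same expected rise, so it cancels: f(6 − b) − f(6 − b) = 0. The simulated rejection rate is 4.5% to 5.4% when both arms comply equally.

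**Wear days.** Criterion 5 starts at 4 days a week, as does section 4.3.4, so that minimum adds no days. Under section 6, a 4-day wearer would have to add one. The contradiction therefore also bears on the artefact if wear is analysed per week.

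**The case against.** The strongest reply is that the plan already holds the right comparison. Section 3 states its wear-time hypothesis between groups, for comfortable wear, and no hypothesis concerns a change from baseline. The 1-month contrast is randomized, and the control-treatment group's change from Visit 1 to Visit 2B shows the effect of the instruction without treatment. All of this stands. What remains is that section 10.1 also lists the three comparisons with baseline as tests of key endpoints, without any limit on what may be concluded from them.

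A reader might infer four stronger things that the documents do not support.

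- *The protocol fixes wear time, so a gain is certain.* Six hours is a minimum that participants agree to try to reach; wear above it is free. Section 8 allows discontinuation for not following procedures but names no wear-hour threshold. No baseline distribution is given, and the table and simulation run from about 5% to nearly 100%.
- *The between-group test is uninformative.* The shared floor can shrink a difference among people who would otherwise wear lenses for less than 6 hours, so sensitivity for average wear time may be reduced. It does not constrain wear above 6 hours, and error stays near 5% under equal compliance.
- *The instruction could reproduce the 4 h/day benefit cited in section 1.* That figure is for comfortable wear; the just-under-4 h limit above is for total wear in one extreme participant.
- *Comfortable wear time is inflated in the same way.* It has no instructed minimum. It is bounded by total wear, so its ceiling may move, but in symptomatic wearers hours added after discomfort begins are not comfortable hours.

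**Conclusion.** The concern holds in limited form. A change from baseline in average wear time cannot be credited to iLux, because the instruction alone can produce one. This applies to the within-group test, the 3-month test in the treatment group, and the pooled test to the extent that its baseline is Visit 1. The size rests on an undocumented share entering below 6 hours and on their compliance: negligible if almost all already wear lenses well above 6 hours, and 0.5 h/day if 25% start at a mean of 4 hours and comply. Comfortable wear time is affected at most indirectly. The primary endpoint and the sample size are untouched. The randomized 1-month comparison is not biased by an instruction given to both arms, on the assumption that both follow it equally; its sensitivity for average wear time may be lower.

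The minimum wear days in sections 4.3.4 and 6 are a plain contradiction, independent of these assumptions.

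**What to change.** In section 10.1:

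1. Make the randomized 1-month between-group comparison, adjusted for Visit 1 wear time, the only inferential efficacy test for average and comfortable wear time.
2. Report within-group, 3-month and pooled wear-time changes descriptively, without significance claims.
3. Beside them, show the control-treatment group's change from Visit 1 to Visit 2B and the share of each group below 6 h/day at Visit 1.
4. State which visit is the control-treatment group's baseline in the pooled data.

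Reconcile the minimum wear days in sections 4.3.4 and 6.

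Two other remedies are tempting but bring their own problems. Hours of uncomfortable wear (total minus comfortable) can make a benefit look like harm: as an illustration, 10 h total with 7 h comfortable gives 3, while 6 h with 4 h gives 2. Restricting the analysis to people at 6 h or more at Visit 1 selects on the baseline value of the outcome and invites regression to the mean.

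The cost is wording. All the data are already collected, and no visit or participant is added. The sponsor gives up an uncontrolled within-group significance claim for wear time.
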